The Patient Health Questionnaire-9 (PHQ-9)¹⁸ will be used to measure depression as another component of health-related quality of life. The PHQ-9 is the depression module of the Patient Health Questionnaire (a self-administered diagnostic instrument for common mental disorders). The 9 items consist of the diagnostic criteria used by the DSM-IV for depressive disorders. The PHQ-9 also measures depression severity. Total PHQ-9 score at baseline and follow-up assessments will be used as dependent measures of depression.

The 7-item Generalized Anxiety Scale (GAD-7) will be used to measure anxiety, which has been demonstrated as an important quality of life outcome in sleep research¹⁹ and may impact PAP adherence. The GAD-7 is a component of the Primary Care Evaluation of Mental Disorders (PRIME-MD) suite of evaluation tools. It was initially developed for evaluation of generalized anxiety disorder, and has also proved useful in screening for other DSM-IV Axis I anxiety disorders. The GAD-7 is a 7-item scale (scores range from 0 to 27), with a cut off score of ≥ 10 yielding both sensitivity and specificity above .80 for GAD. The GAD-7 score at baseline and follow-up assessments will be explored as a dependent measure of anxiety, but we have not included anxiety as a primary outcome measure in sample size calculations and data analysis (see below).

Caregiving questions (21 items). To explore how caregiving impacts an individual's sleep and quality of life, we will include questions from the National Alliance for Caregiving. Questions pertain to the type and amount of caregiving provided.

- Intervention process measures

The Dysfunctional Beliefs and Attitudes about Sleep (DBAS-16) scale, brief version²⁰ will be used to measure participants' sleep-related cognitions. The DBAS-16 uses a Likert-type scale, and was developed from the original 30-item DBAS. Total DBAS-16 scores at baseline and at follow-up assessments will be compared between groups to measure effects of the intervention on participants' beliefs and attitudes about sleep as a measure of the process of the intervention.

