We will use the Self-efficacy (5-item), Knowledge (12-item) and Decisional Balance Index (5-item) subscales from the 54-item scale of behavioral determinants of PAP adherence.²¹ These subscales provide Likert-type (for the Self-efficacy and Decisional Balance Index subscales) or yes/no (for the Knowledge subscale) response options. In prior work, the full scale (measured at 1-week after start of PAP therapy) predicted PAP adherence, and the DBI individually accounted for 17% of the variance in PAP adherence in adjusted analyses. The Self-efficacy, Knowledge and Decisional Balance Index subscale scores will be compared between groups to measure effects of the intervention on participants' beliefs and attitudes about OSA ad PAP.

- Blood sample

One blood sample (8mL) will be drawn by a study phlebotomist at one of 4 possible locations (CRC at West Los Angeles, Building 200 or Building 25 at Sepulveda, or if requested, at a subjects' home. Blood samples will be processed and stored in the CRC or in a laboratory at Sepulveda (Building 7/C10) until transported to the UCLA Cousins Center for Psychoneuroimmunology for analysis. The blood samples will be assayed for proinflammatory cytokines and corresponding acute-phase proteins (i.e., CRP, TNF α , IL-6, IL-8, and IL-10), which are markers of immune system activity.

Sleep Assessment Monitoring (Data Obtained through Monitoring of Participants)

- Objective sleep quality monitoring

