1	1	30 minutes	Introduction; general sleep and OSA education
2	2	30 minutes	Sleep across the lifespan, general health education
3	3	30 minutes	Sleep and health

4	4	30 minutes	Daytime relaxation techniques
6	5	30 minutes	Daytime stress reduction

Post-Treatment and Follow-up Assessments

Post-treatment and follow-up assessments will be performed by research personnel blinded to group assignment. Participants who can no longer travel to VA GLAHS (e.g., moved away, too ill) will be visited at their living location (if < 30 miles away) or interviewed by telephone (if ≥ 30 miles away). Veterans will receive \$25 for each assessment for a possible total of \$100 (i.e., baseline, post-treatment, 3-month and 6-month).

Table 4: Time Points for Data Collection and Measures Used

	Baseline	Post-tx	3-mo	6-mo	12-mo
Data Collected by Research Staff					
Blood sample: assayed for proinflammatory cytokines and corresponding acute-phase proteins (i.e., CRP, TNF α , IL-6, IL-8, and IL-10)	✓	✓	✓	✓	
Medication review	✓	✓	✓	✓	
Data Collected from Participants					
Demographic data	✓				
Mini-Mental State Examination (MMSE)	✓				
Hopkins Verbal Learning Test – Revised (HVLT-R)	✓	✓	✓	✓	
Digit Symbol Substitution	✓	✓	✓	✓	
Trails A and B	✓	✓	✓	✓	
Forward and Backward Digit Span	✓	✓	✓	✓	
Letter-Number Sequencing	✓	✓	✓	✓	
Control Oral Word Association (COWA)	✓	✓	✓	✓	
Geriatric Pain Measure (GPM) intensity subscale	✓	✓	✓	✓	
Restless Leg Syndrome scale (RLS)	✓				
Pittsburgh Sleep Quality Index (PSQI)	✓	✓	✓	✓	✓
Insomnia Severity Index (ISI)	✓	✓	✓	✓	✓
Epworth Sleepiness Scale (ESS)	✓	✓	✓	✓	✓
Patient Health Quest. depression module (PHQ-9)	✓	✓	✓	✓	
12-item Short-form Health Survey (SF-12v2)	✓	✓	✓	✓	
EuroQol-5D scale (EQ-5D)	✓	✓	✓	✓	
PHQ GAD	✓	✓	✓	✓	
PC-PTSD	✓				
Caregiving questions	✓	✓	✓	✓	
Dysfunctional Beliefs & Attitudes about Sleep (DBAS-16)	✓	✓	✓	✓	
PAP Self-efficacy, Knowledge and Decisional Balance Index subscales	✓	✓	✓	✓	
Data from Participant Monitoring					
Wrist actigraphy	✓	✓	✓	✓	
PAP adherence		✓	✓	✓	✓
Follow-up Data from Participant/ Record Review					
Sleep clinic visits		✓	✓	✓	

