We expect that the group by time analysis of covariance for the sleep variables will show a difference between groups, and post-hoc analyses will show increased nighttime sleep efficiency and improved self-reported sleep (indicated by lower PSQI scores) in the intervention group compared to the control group. Following review of graphical representation of our longitudinal results (on main outcome measures), we will use repeated measures ANCOVA models to test both linear and nonlinear (i.e., quadratic) differential changes over time. Post-hoc tests within each time point (using Tukey type 1 error control) will be conducted. We expect there will be no difference between intervention and control groups at baseline, but differences will be present at follow-up. Other participant characteristics will be considered as possible covariates to reduce bias in our estimate of treatment effects and to increase precision. The major covariates that we expect to consider are age, cognition (estimated by MMSE) and comorbidity (estimated by CIRS-G). Other covariates we will consider include specific diagnoses and medications that may interfere with sleep, and measures of the intervention process (DBAS-16 scores, Self-efficacy, Knowledge and Decisional Balance Index subscales).

Sample size calculations were performed for each of the main outcome variables using reported effect sizes and/or calculated effect sizes from reported sample means and standard deviations reported in the literature in prior studies of CBT-I for insomnia and behavioral PAP adherence interventions in outpatient adults (see Table 5). Prior literature indicates that CBT-I is an extremely potent intervention for insomnia, and the studies typically have large effect sizes and small samples. Some caution is warranted, however, since efficacy studies usually employ tightly controlled ‘ideal’ treatment conditions, which also yield larger effect sizes

than effectiveness studies with more ‘real world’ conditions. Regardless of these issues, even the most conservative estimates of effect size from the literature suggest we will have an adequate sample size to test our sleep outcomes. A recent meta-analysis of trials of PAP adherence interventions published as a Cochrane review was used in estimating sample size for the PAP adherence component of our intervention.^{Error! Bookmark not defined.} this analysis suggests we will have an adequate sample size to test our PAP adherence outcomes.

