Hypothesis 4a: Among intervention participants, improvements in beliefs and attitudes about sleep and OSA will be associated with improved nighttime sleep and better PAP adherence at 3- and 6-months follow-up.

Hypothesis 4b: Intervention participants will identify factors that act as facilitators or barriers to their participation and adherence with the intervention.

We will measure (in both the intervention and control groups) participants' beliefs and attitudes about sleep (using the DBAS-16) and OSA and PAP therapy (using the Self-efficacy, Knowledge and Decisional Balance Index subscales). We will test for differences between groups in these scales between baseline and 3-months follow-up using analysis of covariance (as described above under Hypothesis 1). These scales will also be included as covariates in secondary analyses of main study outcomes to address the effect of "dose" of intervention received on particular participant outcomes (e.g., nighttime sleep and PAP adherence). Within the intervention group, we will also review specific aspects of the process of the intervention (e.g., sleep diary data on bedtime, rise time, in-bed time and daytime napping) to further clarify whether key aspects of the intervention were implemented by participants.

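### Belief, knowledge and attitude scores are labelled as the dose of intervention received, while the adherence record that is closer to dose enters no outcome model

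*Combined protocol and SAP*

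**What the plan says.** All references are to the combined protocol and SAP.

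- **Dose analysis.** In the text under Hypotheses 4a and 4b, the description of the DBAS-16 and the three PAP subscales opens "We will measure (in both the intervention and control groups". After planning a between-group ANCOVA of the scales, it adds: "These scales will also be included as covariates in secondary analyses of main study outcomes to address the effect of 'dose' of intervention received". It does not say which arms enter, which visit's scores are used, or whether scores are raw or change from baseline.
- **What the scales are.** The Intervention process measures section says of the DBAS-16: "sleep-related cognitions. The DBAS-16 uses a Likert-type scale". It describes the PAP measures as "subscales from the 54-item scale of behavioral determinants of PAP adherence". Table 1 lists all of them under dependent variables.
- **When they are scored.** In Table 4 the row "PAP Self-efficacy, Knowledge and Decisional Balance Index subscales" is ticked at baseline and at every assessment to 6 months, as is the DBAS-16 row.
- **Adherence data.** The opening overview says adherence to key parts of the intervention is collected in the intervention arm. The Intervention condition section has staff record what they recommended and whether it was followed, so as to document the process.
- **Process review.** Within the intervention arm the plan will also "review specific aspects of the process of the intervention (e.g., sleep diary data on bedtime, rise time, in-bed time and daytime napping", to see whether key elements were put into practice. No outcome is tied to this.
- **Hypothesis 1 covariates.** Among the further covariates to be considered are "measures of the intervention process (DBAS-16 scores, Self-efficacy, Knowledge and Decisional Balance Index subscales", with no restriction to baseline values.

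**The concern.** Dose means how much of the intervention a participant received or carried out. A belief score is a response to the intervention, mixed with whatever the participant already believed. Someone who attends all five sessions with unchanged beliefs would count as low dose. Someone who arrives with favorable beliefs would have a high raw score before session 1. Controls, who receive none of the intervention, would have a score too, and their Knowledge score may rise because the control program itself teaches about insomnia and OSA.

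Two things are at stake. First, a belief-outcome association would be reported as dose-response, while data nearer to dose are collected and left out of every outcome model. That matters for a program designed to balance potency against burden and cost. Second, if follow-up scores enter a model containing both arms, the model adjusts for something the intervention is intended to move. Its group coefficient is then no longer the treatment effect. The Hypothesis 1 covariate list leaves room for this in the sleep analyses.

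**Working it through.** The plan states no figure for this analysis, so there is none to reproduce. The main check is a reading of the text; the arithmetic only shows the possible size.

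**1. Do the scales record receipt?** No. They are described as cognitions and as determinants of PAP adherence, are classed as dependent variables, are tested as between-group outcomes, and exist before any session. In prior work, "the DBI individually accounted for 17% of the variance in PAP adherence in adjusted analyses"; the plan does not link that figure to any amount of intervention. A clear Decisional Balance coefficient could therefore appear here with no variation in dose at all.

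**2. Is the adherence record used?** From the Analysis Plan and Hypotheses section through Potential Shortcomings in the Proposed Analysis, no outcome model names it. The process review under Hypothesis 4 is descriptive. Session attendance is not named as a recorded variable.

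**3. One-arm reading of the scale model.** No group effect is estimated, so nothing is attenuated. The fault is only that an association with beliefs is called dose.

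**4. Two-arm reading with follow-up scores.** Score both variables so that higher is better, in within-arm SD units. Let d be the unadjusted group effect, r the within-arm correlation of belief with outcome, and D the between-arm belief difference. The expected group coefficient is

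d − r × D.

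*PAP adherence.* d = 0.59 or 0.55 (Table 5). r = √0.17 = 0.412, assuming the 17% can be read as a within-arm squared correlation. D is assumed, because the documents give none.

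| D (assumed) | From d = 0.59 | From d = 0.55 |
|---|---|---|
| 0 | 0.59 | 0.55 |
| 0.3 | 0.59 − 0.124 = 0.47 | 0.43 |
| 0.5 | 0.59 − 0.206 = 0.38 | 0.34 |
| 0.8 | 0.59 − 0.330 = 0.26 | 0.22 |

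The stated Hypothesis 1 tests for PAP adherence are a t-test and a chi-square test without covariates, so these rows bear on the secondary model.

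*Actigraphy sleep efficiency.* d = 0.60 (Table 5); r and D are both assumed.

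- r = 0.2, D = 0.3: 0.60 − 0.06 = 0.54
- r = 0.3, D = 0.5: 0.60 − 0.15 = 0.45
- r = 0.5, D = 0.8: 0.60 − 0.40 = 0.20

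These rows are the ones relevant to the Hypothesis 1 sleep ANCOVAs, should follow-up scores be used there.

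**5. What a proper dose analysis could detect.** The plan expects 60 × 0.85 = 51 intervention completers at 6 months. With Fisher's z, 80% power and two-sided .05, the smallest detectable correlation is

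tanh((1.960 + 0.842) / √(51 − 3)) = tanh(0.404) = 0.38.

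**The case against.** The best defense is that this is mostly a matter of labelling. The plan itself puts the word dose in quotation marks and elsewhere consistently calls the scales process measures. Hypothesis 4a is confined to intervention participants and speaks of improvements, so a one-arm, change-score model is at least as natural a reading as a two-arm one, and under it no group effect is distorted. The sentence at issue is also the only stated quantitative model linking the scales to outcomes; deleting it would leave Hypothesis 4a without an analysis. The adherence record has a stated purpose, and the Limitations section already cautions about causal claims for other process aspects. Any replacement dose analysis would be confounded and would detect only moderate correlations.

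Much of this stands. The model should be kept and renamed, and the replacement should be labelled exploratory. What does not stand is the label: quotation marks do not make a belief score a measure of receipt, and the Limitations text neither addresses that reading nor supplies a dose variable.

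A reader might go further and infer that the trial's main treatment effect will be attenuated by the amounts shown above. The documents do not support that. The Potential Shortcomings section makes randomized group the main independent variable, the Hypothesis 1 list only says these covariates will be considered, and nothing says the group coefficient from the secondary model will be reported as the treatment effect.

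**Conclusion.** The point holds as a fault in a secondary analysis. As written, that analysis cannot estimate the effect of dose; it can only show a belief-outcome association, which is what Hypothesis 4a asks. The record closer to dose is collected and not analysed against outcomes. This rests on the text and needs no assumption.

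The size depends on the reading. In a one-arm model it is an error of interpretation only. In a two-arm model with follow-up scores, the PAP group coefficient would fall from 0.59 to between 0.47 and 0.26, and the sleep efficiency coefficient from 0.60 to between 0.54 and 0.20. These are illustrations: the between-arm belief differences and the sleep correlations are assumed, and the 17% comes from adjusted analyses in prior work, so it need not be a within-arm squared correlation.

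The primary intention-to-treat comparisons are unaffected provided follow-up values of these scales are not used as Hypothesis 1 covariates. Nor should it be inferred that Hypothesis 4a is untestable or that the between-group comparisons of the scales are unsound; both can stand.

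**What to change.** 1. **Hypothesis 4a/4b text.** Keep the model linking the scales to sleep and PAP outcomes. State it as the Hypothesis 4a process-association analysis, within the intervention arm, using change from baseline, at 3 and 6 months. Drop the word dose.
2. **Add an exploratory dose analysis in the intervention arm.** Use the existing record of adherence to recommendations, plus the number of the five sessions completed if that is recorded. For the PAP outcome, leave out recommendations to use PAP, since following them is close to the outcome itself. Say that adherence is not randomized, so the result is confounded, and that only correlations of about 0.38 or more are detectable with 80% power at 51 completers. If adherence barely varies, report it descriptively.
3. **Hypothesis 1 covariates.** Allow these scales only at their baseline values. If a two-arm model with follow-up scores is run anyway, state that its group coefficient is not the treatment effect.

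The cost is a few sentences under Hypothesis 4, one clause under Hypothesis 1 and, if attendance is not already captured, one field on the staff record. No new visits, staff or participants are needed.

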As described above, participants will be enrolled from the sleep clinics at VA GLAHS Sepulveda and West Los Angeles campuses. Based on FY11 data, at least 1037 patients per year will be diagnosed with OSA and prescribed PAP (using PAP equipment provided by VA GLAHS). We expect at least 52% will be aged ≥ 50 years, and at least 50% will also meet diagnostic criteria for insomnia. Based on this data, we conservatively estimate that at least 22 Veterans per month will be eligible for the study (i.e., [1037 PAP machines prescribed/12 months] \times [.52 aged ≥ 60 years] \times [.50 meet criteria for insomnia] =22.5). Based on consent rates in our prior VA studies we expect a 50% consent rate among eligible Veterans, which would provide at least 10 enrolled Veterans per month. We estimate that approximately 50% of enrolled participants

will meet all inclusion and exclusion criteria and be randomized, resulting in approximately 5 randomized participants per month, and our total target enrollment will be 120 randomized participants.

We have extensive experience in methods to encourage participant retention. For example, in our ongoing CBT-I trial in older Veterans, one of 122 participants who have reached the 6-month time-point has died, and only an additional 9 participants have been lost to follow-up due to other reasons, resulting in only 8.2% (10/122) loss by 6-months. In the current proposal, we conservatively estimate 15% loss by 6 months, which would result in approximately 102 (51 per group) participants completing the 6-month assessment. However, as in our prior work, we will monitor enrollment and participant loss throughout the study, to allow adjustment of the timeline and/or enrollment and retention procedures if we do not meet targets. As described in the analysis plan below, we will use standard “intention to treat” analysis, and sample size calculations have been made based on this analysis. Sample size calculations for each major outcome measure (described below) suggest that the target sample size will be sufficient to test our major hypotheses. All sample size calculations are based on 80% power and two-tailed P-value < .05.

Analysis Plan and Hypotheses

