The analysis plan for each specific hypothesis is listed below. In addition to hypothesis testing to analyze effects of the intervention on sleep, PAP adherence, depressive symptoms and quality of life, we will develop models showing which covariates predict the values of each of the outcome measures. Prior to hypothesis testing, data will be cleaned, possible outliers identified, and data distributions evaluated for assumptions of analysis (e.g. normality, homogeneity of variance). If necessary, normalized rank transformations as described in Bonate²⁴ will be performed and normalized rank scores will be submitted to analysis.

Hypothesis 1: Compared to control participants, participants randomized to the intervention will have improved nighttime sleep (i.e., higher sleep efficiency, better self-reported sleep) and better PAP adherence (measured objectively) at 3-months follow-up.

This hypothesis tests for differences between the intervention and control groups in our primary outcome measures of nighttime sleep and PAP adherence, between baseline assessment and 3-months follow-up, which is our primary time endpoint. Subjective measures of sleep outcomes will include sleep diary (sleep onset latency, wake after sleep onset [WASO], and sleep efficiency) and sleep quality (PSQI). The objective measure of sleep outcome will be actigraphy (sleep efficiency), and the objective measure of PAP adherence will be downloaded from the PAP smart card (percent of nights with PAP use \geq 4 hours, and mean hours of PAP use per night). All outcomes will be assessed using intention to treat analyses. A 2 X 2 (time X group; where time = baseline or 3-month assessment; and group = intervention or control) analysis of covariance analysis will be used with Bonferroni-corrected post-hoc comparisons to investigate differences between the groups in terms of treatment effects in the sleep variables (where baseline and 3-month follow-up data will be available). For PAP adherence outcomes, there will be no “baseline” data (i.e., PAP adherence data isn’t available until the participant starts PAP therapy), so outcomes between groups will be compared with independent samples t-tests and Chi-square test for difference in proportions.

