There are statistical problems we may encounter in analyses, including the statistical handling of participant dropout, possible differential treatment effects across randomization blocks, and the risk of overfitting the data. To deal with dropouts, we will use standard "intention to treat" analysis. The main independent variable will be whether a participant is in the intervention or control group, rather than whether the participant actually receives the intervention. If the participant rejects the intervention at some point after randomization, but allows us to collect follow-up data, we will use standard "intention to treat" analysis. If the participant stops providing data, we will do analyses using all available data, and then repeat analyses after estimating missing data using an EM (expectation-maximization) algorithm, which is less subject to bias than other methods such as carrying forward the last available value; results from both analyses will be reported. It is important to address dropouts, since those who complete the study may be more compliant or healthier than those who drop out. To understand how "completers" may differ from "dropouts", we will compare their baseline characteristics. Dropout rates and characteristics of dropouts will also be compared between groups.

To address the risk of a differential effect of the intervention between randomization blocks, we will test for a block by group interaction. If one is present (suggesting the treatment is more or less effective for one stratification group over another), the results cannot be pooled, which impacts statistical power. However, we anticipate overall treatment effect will overshadow any differential effects across stratification blocks.

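### The EM repeat analysis has no stated model, no allowance in its standard errors for filled-in values, and no rule on which result decides

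*Combined protocol and SAP*

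**What the plan says.** The section Potential Shortcomings in the Proposed Analysis holds the plan's only text on analysing incomplete outcome data. If a participant stops providing data, the team will analyse all available data and then "repeat analyses after estimating missing data using an EM (expectation-maximization) algorithm, which is less subject to bias than other methods"; carrying the last value forward is the example of a worse method. On how the two sets of results relate, the plan says only that "results from both analyses will be reported". The same section compares the baseline characteristics of dropouts and completers, and compares dropout between groups.

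Under Hypothesis 1 the comparison is "between baseline assessment and 3-months follow-up, which is our primary time endpoint". The sleep outcomes are tested with a 2 × 2 analysis of covariance, "where time = baseline or 3-month assessment; and group = intervention or control". A longitudinal model is added: "Following review of graphical representation of our longitudinal results (on main outcome measures), we will use repeated measures ANCOVA models to test" linear and quadratic change. Nothing is said there about incomplete cases.

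On the amount of loss, Sample size estimates says: "In the current proposal, we conservatively estimate 15% loss by 6 months". The team's ongoing insomnia trial is cited as "resulting in only 8.2% (10/122) loss by 6-months". Loss at 3 months is not given.

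**The concern.** Three things are left open: which variables the EM model contains, how uncertainty in the estimated values reaches the standard errors, and which result decides if the two disagree.

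Estimating missing values and then repeating the analyses reads most naturally as a single fill-in followed by the same tests on 120 apparently complete records. The tests would then count participants who supplied no follow-up value as if they had. If group is in the EM model, the filled values lie exactly on the fitted line and the interval is too narrow. If group is left out, the filled values pull the arms together and the effect is diluted.

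The plan recommends EM for its lower bias and names neither result as primary. A report could therefore rest on the falsely precise or the diluted result without departing from the plan. This mainly concerns questionnaire, diary and actigraphy outcomes. PAP use is retrieved by modem or memory card and is less exposed to missed visits.

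**Working it through.** **Inputs.** From the plan: 60 per group, two-sided .05, and 15% loss by 6 months. The plan's own figures reproduce: 120 × .85 = 102, or 51 per group, and 10/122 = 8.2%. Assumed, because the plan gives no value: 5% as a lower loss level, baseline–follow-up correlation r = .5 (range .3 to .7), and equal random loss in both arms. With m observed per group, the three levels are m = 57 (5%), m = 55 (about 8%) and m = 51 (15%).

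**Group and baseline in the EM model.** The filled values are regression predictions with zero residual. The ANCOVA estimate and the residual sum of squares do not change. The residual degrees of freedom rise from 2m − 3 to 117, and the apparent group size rises from m to 60. Hence, approximately:

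SE ratio (filled / available data) = √[(2m − 3)/117] × √(m/60)

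- m = 57: √(111/117) × √(57/60) = .949
- m = 55: √(107/117) × √(55/60) = .916
- m = 51: √(99/117) × √(51/60) = .848

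The filled test rejects when |t| on 2m − 3 degrees of freedom exceeds 1.980 × ratio, where 1.980 is the .975 point of t on 117 degrees of freedom:

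- m = 57: cut-off 1.880, type I error .063
- m = 55: cut-off 1.813, type I error .073
- m = 51: cut-off 1.680, type I error .096

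Simulation with 10,000 runs per setting (Monte Carlo error about half a point) and r = .3/.5/.7 gives .063/.063/.061, .074/.079/.071 and .096/.093/.097. The available-data test stays at .048 to .053. If the 2 × 2 test is read as a change-score comparison, type I error is .059 to .060, .063 to .068 and .072 to .092.

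**Post-treatment values also in the EM model** (post-treatment seen for everyone, random loss). Type I error depends on the correlation between post-treatment and later values, taken as .5 to .8. It is about 6–7% at m = 55. At m = 51 it is roughly 7–9%, with individual runs between 6.7% and 9.6%. The estimate is no longer identical to the available-data one, and under no effect the p-value rises in roughly 21–45% of trials.

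**Group left out of the EM model** (true d = .60, r = .5).

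| Observed per group | Estimate, baseline only in EM | Coverage of the 95% interval |
|---|---|---|
| 57 | .57 | 94.8% |
| 55 | .55 | 93.9% |
| 51 | .51 | 91.1% |

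Type I error stays at .048 to .052. Power at m = 51 is 93% with either analysis. With earlier visits in the EM model, the estimate at 15% loss is about .53 to .58.

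**Replacements under the same assumptions.** Multiple imputation with Rubin's rules (30 imputations) gives type I error of 4.7% at 8% loss and 5.2% at 15%, with an estimate of .60 and coverage of about 94.5%. A mixed model on the post-treatment, 3- and 6-month values, with baseline as covariate, gives 5.1% at 3 months (5 of 60 lost per arm) and 4.3% at 6 months (9 of 60 lost). Its estimates are about .60 and its coverage 95–96%.

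**The case against.** The strongest reply is that EM comes second. The available-data analysis is listed first, is reported, and holds its level under random loss. Both results are shown and dropouts are described. The 15% figure is a 6-month figure that the plan calls conservative. At the 3-month primary time point loss may be small, because home or telephone assessment is offered to people who cannot travel. At 5% loss the excess is about one percentage point. All of this stands and limits the size of the point.

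A second reply is that EM can do useful work. A reader might infer that the repeat adds nothing about dropout and can only lower the p-value. The documents do not support that, because they do not fix the EM variables. It is true only with group and baseline alone in the EM model and a baseline-adjusted test. Post-treatment values are collected (Table 4), and including them changes the picture. Take loss that depends on post-treatment values in opposite directions by arm, a deliberately strong assumption, with 15% loss, correlation .7 and true d .60. The available-data estimate is then about .74 and the EM estimate .60. Type I error is 12.7% for available data and 8.3% for EM. A repeat analysis is therefore worth having, but even there the EM test does not hold 5%.

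A third reply is that single fill-in is an inference. It is. The plan's wording does not exclude likelihood estimation with proper standard errors, but it does not state it either.

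**Conclusion.** The point holds as a gap in specification with a moderate consequence. Read naturally, the EM repeat analyses filled-in values as observed. With group and baseline in its model, its standard errors are about .95, .92 and .85 of the available-data ones, and type I error is about 6%, 7% and 9–10%, at 5%, 8% and 15% loss. The inflation is smaller when post-treatment values enter. If group is left out, the harm is a diluted estimate and not false positives. These figures rest on equal random loss and an assumed baseline correlation of .5.

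The exposure is mainly at 6 months, under Hypothesis 3. It would be wrong to conclude that the trial's main 3-month test is invalid: the available-data analysis is unaffected by the filling step, and 3-month loss is unstated. The defect is the uncorrected single fill-in and the missing decision rule. Repeating the analysis is not itself at fault. The change should be made, but the trial does not stand or fall on it.

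**What to change.** Replace the EM filling step with one of two methods:

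- multiple imputation with group, AHI stratum, baseline and post-treatment values in the imputation model, combined by Rubin's rules; or
- a likelihood-based mixed model on all collected visits.

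State before unblinding which analysis decides each hypothesis, and label the other as a sensitivity analysis. If the available-data analysis is meant to decide, saying so removes most of the harm. If EM is kept, include group and earlier visits in its model, and use standard errors that allow for the missing values, for example by bootstrap.

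The cost is SAP wording and a little more analysis work. No new data are needed, because the baseline, post-treatment, 3- and 6-month values are already collected. The reported intervals may be slightly wider than those from the filled data.
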